4.7 Removal of Patients from Study Therapy

A patient may be removed from the study therapy for a variety of reasons, including:

- Disease progression that is either symptomatic, rapidly progressive, required urgent intervention, or associated with a decline in performance status
- Unacceptable adverse event(s)
- Intercurrent illness that prevents further participation
- Patient refusal to continue treatment through the study and/or consent withdrawal for study participation
- Patient unable or unwilling to comply with study requirements
- Pregnancy or failure to use adequate birth control
- General or specific changes in the patient's condition that render the patient unacceptable for further treatment in this study in the judgment of the Investigator

Under no circumstance will care of a withdrawn patient be adversely affected by a decision to withdraw or be withdrawn from the study.

4.8 Patient Replacement

Any patient who completes screening and does not receive a dose of ALRN-6924 (single agent cohorts) or at least one dose each of ALRN-6924 and palbociclib (MDM2 amplification and MDM2/CDK4 co-amplification cohort) will be replaced. A patient in the dose escalation portion of the study or a safety run in group who discontinues the study prior to completion of the first cycle for reasons other than safety, or who does not receive all required doses in the first cycle for reasons other than safety, will be replaced. A patient in the dose expansion portion of the study who discontinues study participation prior to the completion of the first cycle of treatment for any reason or who does not receive all required doses in the first cycle may be replaced. Patients who are not confirmed by the central laboratory to have met all molecular requirements for their given cohort may be replaced.

5 TREATMENT PLAN

5.1 Study Drug Description

ALRN-6924

The study drug for ALRN-6924-1-01 is the investigational agent ALRN-6924. Details on the administration, dispensing, return, and destruction of ALRN-6924 will be provided in the Pharmacy Binder.

ALRN-6924 drug product is a frozen or refrigerated liquid product supplied in single-use glass vials in a single dose strength of 75 mg in 5.0 mL, dissolved in 20 mM sodium phosphate, 240 mM trehalose, 300 ppm Polysorbate 20, pH 7.5. Each vial contains recoverable 5.0 mL and is filled with formulated ALRN-6924 to 5.5 ± 0.2 mL. ALRN-6924 for Injection is stored as frozen product at -15° to -25° C or refrigerated product at 2° to 8° C.

Palbociclib

For the Phase 2a cohort with MDM2 amplified or MDM2/CDK4 co-amplified solid tumors, palbociclib will be provided to patients as capsules for oral use.

Palbociclib will be administered on an outpatient basis. Patients will be provided with a diary to record time of palbociclib administration on each dosing day. In order to assess treatment compliance, the numbers of palbociclib capsules that were dispensed and returned by the patient will be recorded. Any dose reductions or interruptions, and the reason for these actions, will also be recorded.

5.2 Preparation of ALRN-6924

Specific instructions for acquisition and storage of ALRN-6924 and preparation of the final dosing solution will be provided in the Pharmacy Binder. Briefly, ALRN-6924 is introduced into an IV infusion bag containing D5W; this will be known as ALRN-6924 Dosing Solution and will be provided by the site pharmacy for administration to the patient. ALRN-6924 Dosing Solution will be labeled with the ALRN-6924-1-01 Patient Identification Number. The investigative staff will confirm this information and its relevancy to the intended patient. The start of the ALRN-6924 infusion must begin within 6 hours of dilution into 250-mL D5W, and the infusion bag shall remain at room temperature until use.

5.3 Study Drug Administration

The investigational agent ALRN-6924 as well as palbociclib (IBRANCE®) will be provided by Aileron and distributed to clinical sites. Patients should begin treatment with study drug within 21 days following the start of clinical screening. Issues that would cause treatment delays should be discussed with Sponsor's Medical Monitor.

Treatment of patients in the dose escalation and the dose expansion phases of the study will continue until unacceptable toxicity, patient or physician decision to discontinue therapy, or disease progression that is either symptomatic, rapidly progressive, requires urgent intervention, or is associated with a decline in performance status. Patients receiving clinical benefit despite evidence of suspected or confirmed PD may continue on study after a discussion between the Principle Investigator and Medical Monitor.

ALRN-6924 will be administered by IV infusion in D5W. The pre-defined dose will be calculated for each patient based on body weight at the start of each cycle. During the first two cycles, ALRN-6924 should be administered in the morning to allow observation of delayed infusion reactions.

Phase 1 Dose Escalation:

Treatment Regimen	Infusion Days	Infusion Time	Additional notes
DR-A	1, 8, 15 of a 28-day cycle	1 hour (± 15 min)	At the end of the infusion, IV fluids (saline) or oral fluids (500 mL – 1000 mL) should be administered, unless clinically contraindicated.
DR-A-2	1, 8, 15 of a 28-day cycle	2 hours (± 15 min)	At the end of the infusion, IV fluids (saline) or oral fluids (500 mL – 1000 mL) should be administered, unless clinically contraindicated. Administer dexamethasone (4 mg orally or IV) approximately 4 hours after the end of the infusion in Cycles 1 and 2, and thereafter at the discretion of the investigator.
DR-B	1, 4, 8, 11 of a 21-day cycle	1 hour (± 15 min)	At the end of the infusion, IV fluids (saline) or oral fluids (500 mL – 1000 mL) should be administered, unless clinically contraindicated.

In DEP, ALRN-6924 will not be administered outside of the planned schedule in Cycle 1 (i.e., there are no planned windows for dose days). Follow-up visits on non-dosing days have windows, however, at the Investigator's discretion, it may be necessary to conduct a study visit on an alternative day than described in this schedule in order to protect the safety, rights, or welfare of the patient. If this is the situation, the Investigator will confer with and obtain approval from the Medical Monitor.

Patients in the DEP who remain on study treatment for 2 years or longer may have their dosing frequency reduced (i.e., Days 1 and 15 of a 28-day cycle for DR-A and Days 1 and 8 of a 21-day cycle for DR-B), at the discretion of the investigator. In the event that disease control is lost, the original administration schedule may be resumed, at the discretion of the investigator.

Phase 2a Dose Expansion:

Treatment Regimen	Drug and Dose Level	Dosing Days	Infusion Time	Additional notes
DR-A	ALRN-6924 3.1 mg/kg	1, 8, 15 of a 28-day cycle	1 hour (± 15 min)	At the end of the infusion, IV fluids (saline) or oral fluids (500 mL – 1000 mL) should be administered, unless clinically contraindicated.
DR-B	ALRN-6924 2.7 mg/kg	1, 4, 8, 11 of a 21-day cycle	1 hour (± 15 min)	At the end of the infusion, IV fluids (saline) or oral fluids (500 mL – 1000 mL) should be administered, unless clinically contraindicated.
DR-C	ALRN-6924 3.1 mg/kg [If 3.1 mg/kg is not well tolerated, lower doses may be tested starting at dose levels of -25%]	1, 3, 5 of a 21-day cycle	1 hour (± 15 min)	At the end of the infusion, IV fluids (saline) or oral fluids (500 mL – 1000 mL) should be administered, unless clinically contraindicated.
Combination with palbociclib	ALRN-6924 3.1 mg/kg [If 3.1 mg/kg is not well tolerated, up to two dose reductions of 25% may be tested]	1, 8, 15 of a 28-day cycle	1 hour (± 15 min)	At the end of the infusion, IV fluids (saline) or oral fluids (500 mL – 1000 mL) should be administered, unless clinically contraindicated.
	Palbociclib 100 mg [If 100 mg is not well tolerated, reduction to a 75 mg dose may be tested.]	1-21 of a 28-day cycle	Oral	Palbociclib should be administered with food. On days when both drugs are administered (Days 1, 8, and 15 of each cycle), palbociclib should be administered at least 6 hours after the infusion of ALRN-6924.

5.4 Management of Toxicities

5.4.1 Toxicities Related to ALRN-6924

Usual supportive medicines used as standard-of-care are allowed, with the exception of growth factors during DEP Cycle 1. All supportive medications and medications to treat toxicities must be recorded in the electronic case report form (eCRF).

5.4.1.1 Management of Infusion-Related Reactions

For the management of Grade 1-2 infusion-related reactions:

- Stop the infusion for 15–30 minutes.
- Measure vital signs at least once every 5 minutes until symptoms abate.
- Consider administering diphenhydramine 25–50 mg IV or equivalent.
- If symptoms abate, re-start the infusion at one-half the previous rate.
- Additional medical measures, such as the administration of selective anti-histamines (e.g., cimetidine 300 mg or ranitidine 50 mg IV) or corticosteroids (e.g., dexamethasone 20 mg IV) may be considered for reactions that do not abate after 15 minutes.
- If symptoms do not abate 30 minutes after the administration of medical measures, discontinue the day's ALRN-6924 treatment.

In the case of a prior infusion-related reaction controlled by above medical management, subsequent ALRN-6924 infusions should include premedication at least 30 minutes before the start of ALRN-6924 infusion.

For the management of Grade 3+ infusion-related reactions:

- Stop the infusion.
- Measure vital signs at least once every 5 minutes until symptoms abate.
- Consider administering the following:
 - Diphenhydramine 50 mg IV
 - Cimetidine 300 mg or ranitidine 50 mg IV
 - Dexamethasone 20 mg IV
 - Epinephrine 0.5 mg SC
 - Albuterol inhaler as needed for bronchospasm
- Additional agents may be administered per institutional guidelines for the treatment of infusion-related reactions.

Patients experiencing Grade 3 hypersensitivity reactions that require hospitalization or any Grade 4 hypersensitivity reactions that are related to ALRN-6924 infusion should be discontinued from study treatment and not rechallenged.

5.4.1.2 Angioedema

Follow standard clinical practice when suspecting angioedema symptoms during treatment with ALRN-6924. If the administration of antihistamines and corticosteroids does not resolve symptoms, consider the administration of icatibant, a bradykinin B2-receptor inhibitor approved in the US and Europe for the treatment of hereditary angioedema. In the event of signs of airway obstruction, epinephrine has to be immediately available and the patient must be in the care of a clinician who can provide emergency airway management.

Patients being treated with ALRN-6924 should be educated about the symptoms of angioedema and urged to tell their care team immediately, should such symptoms develop.

5.4.1.3 Management of Tumor Lysis Syndrome (TLS)

There is a potential for TLS in patients with lymphoma, especially those with large tumor burden, pre-dose elevated lactate dehydrogenase and leukocyte counts, renal dysfunction, or dehydration. TLS can be caused by treatment-induced abrupt cancer cell disintegration. It is usually observed shortly after initiating treatment.

Laboratory TLS is defined as a 25% increase in the levels of serum uric acid, potassium, or phosphorus or a 25% decrease in calcium levels.

Prophylaxis and management of TLS for at risk patients during this clinical trial must include :

- Laboratory assessments of the blood prior to each ALRN-6924 administration during Cycle 1:
 - Electrolytes, including potassium, phosphorus, and calcium
 - Creatinine
 - Uric acid
 - Lactate dehydrogenase
- Administration of allopurinol or an alternative uric acid-lowering agent throughout Cycle 1.
- Antiemetics should be optimized, to prevent poor oral intake and fluid losses from vomiting. Hydration status should be monitored closely and intravenous fluids should be administered as indicated, to prevent or treat dehydration.
- ALRN-6924 must be withheld, if TLS is suspected, and not resumed until electrolyte aberrations and renal function have stabilized and uric acid has been reduced to within normal limits.
- Patients should be hospitalized for closer monitoring and management, if clinically indicated in the judgment of the investigator.

These actions should be continued beyond Cycle 1, if the patient remains at risk, in the judgment of the investigator.

Additional prophylaxis and/or management should be implemented in accordance with local standard of care practices.

5.4.2 Toxicities Related to Palbociclib

For patients in the palbociclib combination cohort, palbociclib-related toxicities should be managed as described in the current approved US prescribing information. All supportive medications and medications to treat toxicities must be recorded in the eCRF.

5.5 Registering and Enrolling Patients on Study, Assignment of Dose Level

5.5.1 Patient Registration

Prior to registration and any study-specific evaluations being performed, adult patients must have given written informed consent; for pediatric patients, written informed consent from parent(s) or legal guardian and pediatric assent for the study must have been provided. All patients must have completed the pre-study evaluations. Patients must meet all of the eligibility requirements listed in [Section 4](#). Each patient will be assigned a unique identification code prior to enrollment.

See the Study Operations Binder for further information on Patient Enrollment.

5.5.2 Staggered Cohort Enrollment Scheme for Dose Level 1 (DEP)

A staggered cohort enrollment scheme will be employed in the first dose cohort (Dose Level 1), in which each patient completes one week of study treatment before the next patient will be enrolled in this cohort. There will be no mandated waiting period between patients enrolled in Dose Level 2 and higher.

5.5.3 Assignment of Dose Level (DEP)

Cohorts of three to six patients will receive ALRN-6924 per dose level and per dose regimen, i.e. DR-A, DR-A-2 and DR-B. At the discretion of the Investigator and Medical Monitor, a fourth patient may be enrolled in the initial group of 3 patients per dose regimen (DR) to help manage patient allocation across multiple sites. If this occurs, the first 3 patients to complete Cycle 1 in the current DR will be used to assess dose limiting toxicities. However, all available data from the 4th patient will be reviewed at the time of the dose level and regimen Safety Review Meeting (Refer to [Section 8.10.1](#)). In the event that a drug-related DLT is observed in one of the first 3 patients of a dose level in a dose regimen, and after discussion among the Investigators and Sponsor's Medical Monitor, additional patients will be enrolled into the study for a total of 6 patients at the same dose level in the same dose regimen.

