5.6 Dose Escalation Criteria (DEP)

In the absence of >33% of patients experiencing a drug-related DLT, escalation to the next dose level for a given treatment arm may proceed when all of the following have occurred:

- At the completion of Cycle 1 (treatment cycle = 28 days for DR-A and DR-A-2 or treatment cycle = 21 days for DR-B),
- The Safety Review Meeting is convened during which the Safety Review Committee (SRC), consisting of the Investigators and Sponsor's Medical Monitor, has reviewed all available safety data for all patients in the cohort and confirms that the next planned dose level is appropriate; and
- The Sponsor Medical Monitor issues written documentation of the decision to proceed to the next planned dose level of a dose regimen.

It is important to note that despite the absence of >33% of patients experiencing a DLT, the next dose level may be less than the planned dose level if the Investigators and Sponsor's Medical Monitor agree that a more conservative dose escalation approach is warranted or would be in the best interest of the patients. The SRC may hold the dose (e.g., stop dose escalation) at their discretion and enroll additional patients until sufficient safety data are obtained to determine escalation of the current dose level or to confirm a certain dose as an MTD or OBD.

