It is anticipated that at least 3 patients will be treated at each dose level per treatment arm. If no patients experience a DLT, then the subsequent 3 patients will be treated at the next planned dose level.

If DLT is observed in ≥ 2 of 3 patients in either treatment DRs at any dose level, no further dose escalation will occur in that DR, and the current dose will be defined as the maximum administered dose (MAD).

If DLT is observed in 1 of 3 patients in a cohort at any dose level, then up to 6 patients total will be enrolled at that same DR at that dose level. If DLT is observed in ≥ 2 patients in the expanded cohort, then no further dose escalation will occur, and the current dose will be defined as the MAD, unless the SRC decides that there is sufficient clinical uncertainty about the DLTs that warrants the enrollment of up to 6 additional patients. In the event of additionally enrolled patients, if a DLT is observed in 33% or more DLT-evaluable patients in the entire cohort, then no further dose escalation will occur, and the current dose will be defined as the MAD for the dosing regimen under consideration. After the MAD is defined, either the previously administered lower dose will be expanded to a total of 6 patients, or an intermediate (between the MAD and the next lower dose level) will be investigated in up to 6 patients. The highest dose tolerated without DLT in at least 5 of 6 patients (i.e. <33% of DLT-evaluable patients experiencing a DLT) in a cohort from one treatment arm will be defined as the MTD for that treatment arm. Additional patients may be added to further explore the MTD or OBD prior to expansion.

Based on review of available safety and PK data during this and other studies with ALRN-6924, dose escalation or modification steps may be adjusted (i.e. increased or decreased) by the SRC to limit the number of patients exposed to sub-therapeutic dose levels as well as to ensure patients' safety. Additional patients may be added to further explore safety at a dose level or to confirm a certain dose as an MTD or OBD.

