5.9.3 Definition of Maximum Tolerated Dose

The MTD is defined as the dose at which ≤ 1 of 6 patients experiences a treatment-related toxicity that qualifies as a DLT, with the next higher dose having ≥ 2 of up to 6 patients experiencing a DLT.

The MTD will not be established until all patients enrolled in the cohort have completed Cycle 1, discontinued treatment or had a dose reduction. Previously established tolerability of a dose level will be reevaluated if toxicities that would have been DLTs in Cycle 1 are observed in later cycles.

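### When a fourth patient is enrolled, section 5.5.3 selects the three patients counted for DLTs by completion of Cycle 1, so a DLT patient who stops or is delayed can fall outside the formal count

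*Protocol*

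**What the plan says.** Protocol 5.5.3 allows one extra patient in the initial group of three, to ease allocation across sites. When that happens, "the first 3 patients to complete Cycle 1 in the current DR will be used to assess dose limiting toxicities". The next sentence adds that "all available data from the 4th patient will be reviewed at the time of the dose level and regimen Safety Review Meeting". The section then ties enlargement to six patients to a DLT in one of the first three.

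The escalation rules elsewhere are not limited to completers:

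- Section 5.7.1: "If no patients experience a DLT, then the subsequent 3 patients will be treated at the next planned dose level". Also: "If DLT is observed in 1 of 3 patients in a cohort at any dose level, then up to 6 patients total will be enrolled".
- The synopsis text on dose escalation and section 8.10.1 likewise make escalation depend on the absence of a DLT. Section 5.9.2 says that DLTs arising in Cycle 1 inform escalation.
- Section 5.6 sets a different condition: "In the absence of >33% of patients experiencing a drug-related DLT".

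Two further sections deal with patients who do not finish the cycle. Under 4.8, a dose-escalation patient "who does not receive all required doses in the first cycle for reasons other than safety, will be replaced". Under 5.9.3, "The MTD will not be established until all patients enrolled in the cohort have completed Cycle 1, discontinued treatment or had a dose reduction".

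The term DLT-evaluable appears in the synopsis and in sections 5.7.1 to 5.7.3 but is defined in neither document. SAP 8.2 reports the number and percent of subjects with DLTs by category and names no denominator. SAP 5.1 assigns the Safety Population (everyone dosed) to safety analyses. SAP section 5 has no DLT analysis set.

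**The concern.** The three counted patients are picked by an event that toxicity can prevent or postpone. Section 5.8.1 requires discontinuation after a related Grade 4 event, with listed exceptions, and allows a delay of up to two weeks after a related Grade 3 event. A patient with a DLT may therefore never complete Cycle 1, or may complete it after the other three. With four enrolled, the count then falls on the three who tolerated the dose.

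Determining the DLTs and the MTD is a primary objective of Phase 1 (section 2.1.1), and the count of three is what the 3+3 rules act on. The denominator should not depend on whether the patient had the event being counted.

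**Working it through.** The plan states no operating characteristics for its 3+3 rule, so there is no figure to reproduce. The check has two parts.

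**1. One cohort, read by each section.** Four are enrolled. One has a DLT and is discontinued in Cycle 1. Three complete it without a DLT.

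| Source | Reading |
|---|---|
| 5.5.3, literal | 0 of 3; the fourth patient's data are reviewed |
| 5.7.1, synopsis, 8.10.1 | the cohort has a DLT, so the no-DLT route to the next dose is not met |
| 5.9.2 | a Cycle 1 DLT informs the decision |
| 5.6 | 1/4 = 25%, below the 33% threshold |
| 4.8 | the patient left for safety, so is not replaced |
| 5.9.3 | a patient who discontinued is among those the MTD waits for |

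Sections 4.8 and 5.9.3 suggest that safety dropouts were meant to count. Neither says that such a patient enters the count when four are enrolled.

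**2. How often the count reads 0 of 3.** Two inputs are assumed, because the documents give neither:

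- p, the true Cycle 1 DLT rate;
- q, the share of DLT patients who do not complete Cycle 1.

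Other patients are taken to complete in enrolment order. The count is 0 of 3 in two ways:

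- Nobody stops, the first three have no DLT, and the fourth is anyone who completes: (1−p)³(1−pq).
- Exactly one of the four stops with a DLT and the other three have none: 4pq(1−p)³.

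The sum is (1−p)³(1+3pq). A DLT patient who is delayed and finishes last has the same effect on this probability as one who stops, so q can also be read as covering delay.

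At p = 0.33, (1−p)³ = 0.67³ = 0.3008:

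- q = 0.25: 0.3008 × 1.2475 = 0.375
- q = 0.5: 0.3008 × 1.495 = 0.450
- q = 1: 0.3008 × 1.99 = 0.599

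The comparators are an ordinary three-patient cohort, (1−p)³ = 0.301, and counting all four, (1−p)⁴ = 0.202.

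| p | all four count | three enrolled | literal, q=0.25 | q=0.5 | q=1 |
|---|---|---|---|---|---|
| 0.20 | 0.410 | 0.512 | 0.589 | 0.666 | 0.819 |
| 0.25 | 0.316 | 0.422 | 0.501 | 0.580 | 0.738 |
| 0.33 | 0.202 | 0.301 | 0.375 | 0.450 | 0.599 |

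The second term, 4pq(1−p)³, is the chance that the cohort reads 0 of 3 while a stopped DLT patient is left out. At p = 0.33 it is 0.099, 0.199 and 0.397 for q = 0.25, 0.5 and 1.

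**The case against.** The strongest reply is that escalation does not rest on three completers. Sections 5.7.1, 5.9.2 and 8.10.1 look to any Cycle 1 DLT in the cohort. Section 5.6 has the Safety Review Committee review every patient, confirm the next dose and hold it if it wishes. This stands as a limit on the harm: the event is lost from the formal count, not from view. It does not remove the problem, because 5.5.3 separates the three patients used for the assessment from the one whose data are reviewed, and committee discretion is not a counting rule.

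Completing Cycle 1 might also mean only reaching Day 28 or Day 21. That is possible, but 5.9.3 lists completing the cycle and discontinuing as separate outcomes, which favours the literal reading. It is also fair that 5.5.3 itself foresees a DLT among the first three, and that 5.8.1 ties mandatory stopping to Grade 4 events. A share of q = 1 is therefore an upper bound, not an expectation.

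A reader might go further in three ways that the documents do not support:

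- **The MTD is biased.** The fourth-patient rule covers only the initial group of three. The MTD rests on up to six patients, waits for those who discontinued, and has its tolerability re-evaluated if later-cycle toxicities would have qualified as DLTs (5.9.3).
- **Patients were escalated past a toxic dose.** Nothing in the documents shows that the situation arose. Sections 5.7.1 and 5.7.2 report DR-A and DR-A-2 each closed to escalation after two DLTs, and one DLT in six DLT-evaluable patients at DL-6A.
- **The SAP's DLT percentage omits these patients.** The Safety Population already contains them.

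**Conclusion.** The concern holds as a defect in the counting rule. Section 5.5.3 states a rule that can exclude a DLT patient, it disagrees with 5.7.1, 5.9.2 and 8.10.1, and no section expressly puts that patient back. It is more likely a drafting fault than an intended rule.

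The size depends on assumed p and q. At p = 0.33, the chance of a 0-of-3 count rises from 0.301 to between 0.375 and 0.599 as q runs from 0.25 to 1. The increase applies only to initial cohorts with a fourth patient. Because DR-A and DR-A-2 escalation has closed, what remains is any further DR-B escalation (which the documents do not describe as closed) and how the DLT results are reported. It should be corrected, but it does not by itself call the selected dose into question.

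**What to change.** 1. Define DLT-evaluable once, in section 5.9, so that any treated patient with a Cycle 1 DLT counts whether or not Cycle 1 was completed. Patients without a DLT count if they complete the cycle with the required doses, consistent with 4.8. Replace the sentence in 5.5.3 with a reference to that definition, covering the fourth patient.
2. Reconcile 5.5.3, 5.6, 5.7.1 and 8.10.1 on what follows a DLT in a four-patient cohort. One of four is 25%, below the threshold in 5.6, while 5.7.1 speaks of 1 of 3 and 8.10.1 requires no DLT. Which action applies is for the sponsor and the Safety Review Committee; the text should state one.
3. Name the denominator in SAP 8.2. If it is the Safety Population, say so, and note that it also includes patients replaced under 4.8. If it is the DLT-evaluable set, add that set to SAP section 5.

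The cost is alignment of several protocol sections and the SAP, not a single sentence. An escalation decision may occasionally wait for the fourth patient to finish Cycle 1.
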